#### **7.5 Other Safety Measures**

Data for COVID-19 clinical features will be listed and tabulated by treatment group.

Data for hospital interventions will be listed and summarized by presenting frequency counts and percentages for each category. The duration (number of days) of extracorporeal support and inotropes/vasopressors administration will be calculated based on the start/stop dates recorded on the eCRF and summarized descriptively. Subjects who were never on extracorporeal support or inotropes/vasopressors will be included in the descriptive summary with a value of zero days of duration.

Body weight assessments will be summarized by presenting descriptive statistics of raw data and change from baseline values at each time point by treatment group.

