#### 4.6 Data Derivations and Transformations

The following derivations will be used in this study:

Study Day:

- Date of assessment – date of randomization + 1 for assessments done on or after date of randomization
- Date of assessment – date of randomization for assessments done before date of randomization

Baseline Observation: the last non-missing value prior to randomization.

Duration:

- Duration in days = end date – start date + 1
- Duration in minutes = end time in minutes – start time in minutes

Origin or Start Date for Time to Event Endpoints:

- Time to death: date of randomization
- Time to ICU Discharge (actual and medical equivalence, if applicable): date of randomization or date of ICU admission, whichever was later
- Time to Hospital Discharge (actual and medical equivalence, if applicable): date of randomization
- Time to Clinical Response: date of randomization

Event Date for Time to Clinical Response:

- If a subject met the criteria for clinical response at multiple assessments, the date of the first assessment meeting the definition of clinical response will be used as the event date for deriving time to clinical response.

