### **Duration of ICU stay (Actual and Medical Equivalence)**

The duration (number of days) of ICU stay from post-randomization through Day 29 will be calculated based on ICU admission and discharge (actual and medical equivalence) dates recorded on the eCRF. Number of days in the ICU will be compared between treatment groups using an ANOVA model, including number of days in the ICU as a dependent variable and treatment group as a fixed effect. From this model, the LS means and 95% CIs for each treatment group, the treatment difference in the LS means, the 95% CI for the difference, and the associated p-value will be presented. If appropriate, an ANCOVA model may instead be used to additionally adjust for baseline characteristics such as age and gender.

Subjects who died while in the ICU will be assigned as in the ICU for the number of days remaining from the day of death to Day 29 for the analysis. Subjects who were at ICU at study completion will be assigned an ICU end date equals to the date of completion for the purpose of deriving the number of ICU days.

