### **Duration of mechanical ventilation**

The duration (number of days) on mechanical ventilation from post randomization through Day 29 will be calculated based on the start/stop dates of mechanical ventilation recorded on the eCRF All Visits page “General Duration of Hospitalization, & Overall Requirement for Mechanical Ventilation, ICU Admission and/or Oxygen Supplementation”. Number of days on mechanical ventilation will be compared between treatment groups using an ANOVA model, including number of days on mechanical ventilation as a dependent variable and treatment group as a fixed effect. From this model, the LS means and 95% CIs for each treatment group, the treatment difference in the LS means, the 95% CI for the difference, and the associated p-value will be presented. If appropriate, an ANCOVA model may instead be used to additionally adjust for baseline characteristics such as age and gender.

Subjects who died during the hospitalization without a stop date of mechanical ventilation recorded on the eCRF will be assigned as being on mechanical ventilation for the number of days remaining to Day 29 for the analysis. Subjects who had mechanical ventilation ongoing at study completion will be assigned a mechanical ventilation end date equals to the date of completion for the purpose of deriving duration of mechanical ventilation. Subjects who are never placed on mechanical ventilation through Day 29 will be included in the analysis with a value of zero days on mechanical ventilation.

A listing of all mechanical ventilation and oxygen administration data collected throughout the study will be provided.

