### **Duration of Hospitalization (Actual and Medical Equivalence)**

The duration (number of days) of hospitalization from post-randomization through Day 29 will be calculated based on hospital admission and discharge (actual and medical equivalence) dates recorded on the eCRF. Number of days in the hospital will be compared between treatment groups using an ANOVA model, including number of days in the hospital as a dependent variable and treatment group as a fixed effect. From this model, the LS means and 95% CIs for each treatment group, the treatment difference in the LS means, the 95% CI for the difference, and the associated p-value will be presented. If appropriate, an ANCOVA model may instead be used to additionally adjust for baseline characteristics such as age and gender.

Subjects who died while in the hospital will be assigned as in the hospital for the number of days remaining from the day of death to Day 29 for the analysis. Subjects who were in the hospital at study completion will be assigned a hospitalization end date equals to the date of completion for the purpose of deriving the duration of hospitalization.

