#### 7.2.1 Treatment-emergent Adverse Events

For summary purposes, AEs will be classified as treatment-emergent AEs (TEAEs) or non-treatment-emergent AEs (non-TEAEs) depending on the comparison of AE onset date/time with the date of randomization. A TEAE will be defined as an AE which occurred on or after the date of randomization. For adverse events with incomplete start dates/times, the same imputation algorithm for missing or partial date/time information as described in Section 5.6 will be used for the determination of an AE being treatment emergent or not. Briefly, the unknown portions of an AE onset date/time will be imputed to the latest possible before being compared to the date of randomization.

Non-TEAEs will be summarized separately from TEAEs by SOC and PT for each treatment group and overall.

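### SAP 7.5 sets no randomisation-to-Day-29 window for vasopressor/inotrope and extracorporeal-support days, and its intervention counts do not separate ongoing from new support

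*SAP*

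**What the plan says.** SAP 7.5 (Other Safety Measures) has three relevant sentences.

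- Counts: "Data for hospital interventions will be listed and summarized by presenting frequency counts and percentages for each category".
- Durations: "The duration (number of days) of extracorporeal support and inotropes/vasopressors administration will be calculated based on the start/stop dates recorded on the eCRF".
- Zero days: "Subjects who were never on extracorporeal support or inotropes/vasopressors will be included in the descriptive summary with a value of zero days of duration".

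None of them mentions randomisation or Day 29. There is also no rule for a subject who dies on support or is still on it at the end. The only general formula, in SAP 4.6, is "Duration in days = end date – start date + 1", which does not truncate.

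Other sections of the SAP do set a window:

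- Ventilation (6.2): "The duration (number of days) on mechanical ventilation from post randomization through Day 29 will be calculated".
- ICU stay (6.2): "The duration (number of days) of ICU stay from post-randomization through Day 29".
- Hospital stay (6.2): "The duration (number of days) of hospitalization from post-randomization through Day 29".
- Adverse events (7.2.1): "A TEAE will be defined as an AE which occurred on or after the date of randomization".

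Oxygen days in 6.2 run from Day 1 to Day 29, and 6.2 has rules for death and for support still running at study completion.

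**The concern.** Subjects can be on these supports before randomisation. Protocol 5.1 allows up to 48 hours of ICU treatment before entry. In Protocol 5.2, exclusion 4 covers shock that is unresponsive and comes with multiorgan failure judged irreversible, and exclusion 14 covers low blood pressure that does not respond to vasopressors. A subject who is responding to vasopressors is not excluded by these criteria, and no criterion names ECMO.

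If SAP 7.5 is programmed as written, days before randomisation are added to that subject's duration. In any table of subjects ever on a support, that subject looks the same as one who first needed it after an infusion.

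The distinction matters for safety. Section 7 of the SAP lists hospital interventions among the safety assessments, and Section 4 has results summarised by treatment group. Protocol 2.2 and 8.3.1 list a fall in blood pressure, and transfusion-related acute lung injury with hypotension, as possible reactions to IVIG, so newly started circulatory support is a plausible sign of harm. The SAP Section 7 methods also apply to the interim safety analysis after about 50 subjects.

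**Working it through.** The plan gives no figure for these measures and no power calculation, so there is nothing to reproduce. From the documents: about 100 subjects randomised 1:1, so 50 per arm, and the SAP 4.6 formula. Every rate below is an assumption, because the documents do not give baseline use.

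**Effect of the formula on one subject**

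- Support starts 1 day before randomisation and stops on Study Day 3. Number the randomisation date 0, so the start is −1 and the stop is 2. As written: 2 − (−1) + 1 = 4 days. Counted from randomisation: 2 − 0 + 1 = 3.
- Support starts 2 days before and stops on the randomisation date. As written: 0 − (−2) + 1 = 3 days. Counted from randomisation: 1.

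**Effect on mean days**

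Assume a share b already on support in each arm, new starts of 20% (SMT) v 40% (IVIG) among the rest, mean days on support after randomisation of 4 v 6, and 1 or 2 prior days (mean 1.5) for those already on it. Mean days are [b + (1 − b) × new-start risk] × mean duration, plus 1.5b if prior days are included.

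At b = 20%:

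- From randomisation: 0.36 × 4 = 1.44 v 0.52 × 6 = 3.12. Difference 1.68, ratio 2.17.
- As written: 1.74 v 3.42. Difference 1.68, ratio 1.97.

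The prior days add the same amount to both arms on average, so the difference does not move. A simulation of the same set-up with durations capped at 29 days gives:

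| Baseline use b | Difference (both ways) | Ratio, from randomisation | Ratio, as written | SMT SD, from randomisation | SMT SD, as written |
|---|---|---|---|---|---|
| 20% | 1.68 | 2.16 | 1.96 | 2.83 | 3.15 |
| 40% | 1.75 | 1.84 | 1.65 | 3.19 | 3.62 |
| 60% | 1.81 | 1.67 | 1.50 | 3.41 | 3.82 |

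**Effect on a count of subjects ever on support**

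Let p be baseline use and r the risk of a new start among subjects not on support, assumed 15% (SMT) v 30% (IVIG). Ever use = p + (1 − p)r, so the difference between arms is (1 − p) × 15 points.

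| Baseline use p | SMT | IVIG | Difference (points) | Ratio |
|---|---|---|---|---|
| 0% | 15.0% | 30.0% | 15.0 | 2.00 |
| 5% | 19.25% | 33.5% | 14.25 | 1.74 |
| 35% | 44.75% | 54.5% | 9.75 | 1.22 |
| 50% | 57.5% | 65.0% | 7.5 | 1.13 |

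Among subjects not on support at randomisation, the difference stays at 15 points and the ratio at 2.00 whatever p is.

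**Chance imbalance at baseline**

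The SD of the difference in baseline use is √(2p(1 − p)/50): 8.0 points at p = 20%, 9.5 at 35%, 10.0 at 50%. Because ever use = r + p(1 − r), it carries over multiplied by (1 − r), which is 0.70 to 0.85. The range is 8.0 × 0.70 = 5.6 to 10.0 × 0.85 = 8.5 points, or roughly 6 to 9.

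**The case against.** The case for leaving the text alone has real content.

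- The eCRF is not in the documents, and neither schedule of procedures has a row for vasopressors, ECMO or hospital interventions. A form limited to post-randomisation data cannot be ruled out. SAP 4.3 summarises data by nominal visit, so the counts might be laid out by visit with Day 1 separate. A reader might infer that the plan presents baseline support as a post-treatment outcome; the documents do not establish that, and SAP 7.5 never labels these tables post-treatment. This stands, and the finding is conditional on it.
- These are not the trial's safety endpoints, and SAP Section 7 rules out formal testing. A reader might infer that a key safety conclusion is at risk; it is not.
- New harm is also seen elsewhere: treatment-emergent events from randomisation, change in SOFA (which scores vasopressor dose), change on the ordinal scale, and vital signs. This stands in part. SOFA is scored only on Days 1, 5, 15 and 29, so support started and stopped in between is missed. Ordinal category 2 pools ECMO with invasive ventilation, so ECMO begun in a ventilated subject leaves the score unchanged.
- A reader might infer that the comparison of days is biased, or that baseline imbalance passes into ever use in full. Neither follows: prior days balance on average, and imbalance is reduced by the factor (1 − r).
- Baseline use might be low, since entry requires only supplemental oxygen and a decision that ICU admission is warranted. At 5% the loss is 0.75 of a point, which is negligible.

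**Conclusion.** The gap is in the text and departs from the SAP's own practice in 6.2 and 7.2.1. Unless the eCRF collects only post-randomisation data, the durations include days that treatment could not have influenced. The cost is extra noise and an attenuated ratio (for example 2.16 to 1.96 at an assumed 20% baseline use), with no bias in the absolute mean difference.

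The counts are the weaker part. If they are tabulated as ever used, an assumed 15-point excess in new use shows as anything from about 14 points to 7.5 over assumed baseline use of 5% to 50%. Chance imbalance adds an SD of roughly 6 to 9 points if baseline use is 20% to 50%. These sizes rest wholly on assumed rates. Because the tables are descriptive and supportive, this is a minor-to-moderate improvement that is cheap to make.

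**What to change.** Amend SAP 7.5 in two places.

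1. Count inotrope/vasopressor days and extracorporeal-support days from the date of randomisation through Day 29, and handle death and support still running as SAP 6.2 does.
2. For these two supports, where SAP 7.5 says start dates are recorded, add a table by arm of new starts after randomisation among subjects not on that support at randomisation. Show support at randomisation as a baseline characteristic by arm. Keep the overall-use table, so that prolonged need in subjects already on support is not lost.

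If the eCRF already restricts collection to post-randomisation data, one sentence saying so settles the prior-days question; the Day 29 end and the rules for death and ongoing support would still need stating.

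Cost: a few sentences and a date filter, with no new data for these two supports. The new-start table has a smaller denominator (for example 50 × 0.65 = 32.5 per arm at 35% baseline use). Other intervention categories can be split only if dates or visit-level records exist for them, which the documents do not show.

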### **8. INTERIM ANALYSES**

An interim analysis will be conducted after 50 subjects (approximately 25 per group) for safety variables through Day 29. Due to the exploratory nature of this phase 2 study, the multiplicity adjustments will not be considered. This interim evaluation simply represents Sponsor safety due diligence. This interim analysis will analyze safety variables including, but not limited to, the following: adverse events (see Section 7.2), clinical laboratory parameters (see Section 7.3), and vital signs (see Section 7.4). The relevant methods described in Section 7 (Safety Analysis) of this SAP intended for the final analysis will also be applicable to the interim analysis.

### **9. SAMPLE SIZE AND POWER CALCULATIONS**

Because of the urgency and lack of previous prospective COVID-19 data, sample size estimation remains incompletely defined; however the size of this pilot study is commensurate with other Phase 2 investigations ongoing during the COVID-19 pandemic. Approximately 100 subjects are allowed to be randomized as part of a humanitarian effort against COVID-19.

## 11. APPENDIX

### 11.1 Appendix A: Schedule of Events

Study Period	Screen/ Baseline	1 st IP	SMT and Daily Evaluations									Follow- Up	Follow-Up Clinic Visit Day		Phone Checks	
			2	3	4	5±1 day	6	7	8	9	10		11-14 Daily if in hospital	15±1 * day	16-28 Daily if in hospital	29±1 * 1 day
Study Day	1															
Procedures/assessments																
Informed consent	X															
Inclusion/exclusion criteria	X															
Demography (age [year of birth], age at screening [years], gender [if female, fertility status], race, and ethnicity), disease characteristics (date of exposure, date of onset a )	X															
Pregnancy test b	X															
Ordinal Scale (at the 1st assessment of a given day) c	X		X	X	X	X	X	X	X	X	X	X	X	X	X	
National Early Warning Score (NEWS) Appendix 2	X		X	X	X	X	X	X	X	X	X	X	X	X	X	
Clinical features key symptoms: fever, cough, shortness of breath, fatigue, myalgia etc.	X		X	X	X	X	X	X	X	X	X	X	X	X	X	
Vital signs (temperature, systolic and diastolic blood pressure, pulse, respiratory rate)	X	X d	X d	X d	X d	X d	X	X	X	X	X	X	X	X	X	
Initial Body Weight for determining all IVIG doses if randomized to combination arm	X															
Body weight for assessing fluid balance twice daily (at least 8 hours)		X	X	X	X	X										

## Schedule of Events (Continued)

Study Period	Screen/ Baseline	1 st IP	SMT and Daily Evaluations										Follow- Up	Follow-Up Clinic Visit Day		Phone Checks		
			1	2	3	4	5±1 day	6	7	8	9	10		11-14 Daily if in hospital	15±1 day	16-28 Daily if in hospital	29 a,f ± 1 day	Day 60 ± 2 days
Study Day																		
Procedures/assessments			1	2	3	4	5±1 day	6	7	8	9	10	11-14 Daily if in hospital	15±1 day	16-28 Daily if in hospital	29 a,f ± 1 day	Day 60 ± 2 days	Day 90 ± 2 days
should separate the time from the first recorded weight)																		
Record result of historical SARS-CoV-2 PCR (qualitative RT-PCR) or other FDA-approved or regulatory-authority-approved diagnostic assay in any specimen during the current hospital admission prior to randomization (eligibility criterion)		X																
Record any supplemental oxygen administration (type, %, flow start/end date/time)	X		X	X	X	X	X	X	X	X	X	X	X	X	X	X	X	
Record any mechanical ventilation (start/end date/time)	X		X	X	X	X	X	X	X	X	X	X	X	X	X	X	X	
Record oxygen saturation (specify on or off oxygen supplementation)	X		X	X	X	X	X	X	X	X	X	X	X	X	X	X	X	
Randomization (after all Screen/Baseline assessments complete)	X																	
Combination arm: Gamunex-C 2 g/kg (total) may be given either as 500 mg/kg in divided doses over 4 consecutive days OR 400 mg/kg in divided doses over 5 consecutive days			X b	X b	X b	X b	X b											

## Schedule of Events (Continued)

Study Period	Screen/ Baseline	1 st IP	SMT and Daily Evaluations										Follow-Up	Follow-Up Clinic Visit Day		Phone Checks
			2	3	4	5±1 day	6	7	8	9	10	11-14 Daily if in hospital		15±1 day	16-28 Daily if in hospital	29 a,f ± 1 day
Study Day	1															
Procedures/assessments																
Record hospital admission and discharge dates	X														X b	
Record ICU admission & discharge dates	X														X b	
Sequential Organ Failure Assessment (SOFA) score (Appendix 4)	X					X							X		X	
Assessment of ARDS (Berlin Criteria) (Appendix 3)	X					X							X		X	
Daily 24-hour fluid balance (intake and output) while in hospital	X	X	X	X	X	X	X	X	X	X	X					
Respiratory sample for quantitative measurement of SARS-CoV-2 viral load by NAT or PCR (real-time RT-PCR) (obtained via nasopharyngeal swab)	Pre randomized treatment i					X i							X		X	
Sample for quantitative measurement of IgM and IgG antibodies to SARS-CoV-2 (store serum samples frozen at -70°C for later analysis at an external lab)	Pre randomized treatment i					X i							X		X	
Serum Chemistry (creatinine, albumin, alanine aminotransferase [ALT], total bilirubin, lactate dehydrogenase [LDH])	Pre randomized treatment i					X i							X		X	

## Schedule of Events (Continued)

Study Period	Screen/ Baseline	1 st IP	SMT and Daily Evaluations										Follow- Up	Follow-Up Clinic Visit Day			Phone Checks	
			1	2	3	4	5±1 day	6	7	8	9	10		11-14 Daily if in hospital	15±1 day	16-28 Daily if in hospital	29 a,f ± 1 day	Day 60 ± 2 days
Study Day Procedures/assessments																		
Ferritin, CRP, D-dimer	Pre randomized treatment i						X j							X		X		
Hematology: absolute lymphocyte count and standard hematology (hemoglobin, hematocrit, platelet count, leukocyte count with differential)	Pre randomized treatment i						X j							X		X		
Direct antiglobulin test (DAT)	Pre randomized treatment i						X j							X		X		
Cytokine panel j	Pre randomized treatment i						X j							X		X		
Record SAEs and TEAEs d	X	X	X	X	X	X	X	X	X	X	X	X	X	X	X	X	X	
Record standard care concomitant medications	X	X	X	X	X	X	X	X	X	X	X	X	X	X	X	X	X	
Phone Checks for Vital Status (living or deceased), any hospital readmissions or SAEs/non-serious AEs after Day 29 Final Clinic Visit																	X	X

a Date of first contact with the virus, date of first symptoms, date of PCR (RT-PCR)/other FDA approved- or regulatory-authority-approved diagnostic assay positive

b Human chorionic gonadotropin-based assay for women of childbearing potential (urine matrix is also valid).

## Schedule of Events (Continued)

- c Ordinal scale measure of clinical status: 1) Death; 2) Hospitalized, on invasive mechanical ventilation or ECMO; 3) Hospitalized, on non-invasive ventilation or high flow oxygen devices; 4) Hospitalized, requiring supplemental oxygen; 5) Hospitalized, not requiring supplemental oxygen; 6) Not hospitalized, limitation on activities; 7) Not hospitalized, no limitations on activities.
- d Grade 3-5 TEAEs and potentially related TEAEs through Day 29 will be defined according to CTCAE criteria, US Department of Health and Human Services, NIH, and NCI. In this clinical study, disease progression is defined as the worsening of a subject's condition attributable to the disease for which the investigational product is being studied. It may be an increase in the severity of the targeted disease and/or increases in the symptoms of the targeted disease. Anticipated symptoms of COVID-19 include fever, cough, hypoxia, dyspnea, hemoptysis, myalgia, fatigue, pharyngitis, which may develop at any time during the course of the disease. The development of COVID-19 symptoms during the clinical study should not be recorded as individual TEAEs, unless there is evidence suggesting a causal relationship between IVIG and the TEAE.
- e Procedures/assessments for indicated visits may be performed at the study site or, if deemed appropriate, at an alternate site (e.g., subject's residence, local healthcare professional's site) under the care and supervision of trained healthcare personnel.
- f Final Clinic Visit, followed by Phone Checks.
- g The total net dose is 2 g/kg body (maximum of 160 g for subjects weighing more than 80 kg). The first infusion is on Day 1. At the discretion of the Principal Investigator, the 2 g/kg net total dose may be divided either into (a) infusions of 500 mg/kg body weight over 4 days OR (b) 400 mg/kg body weight over 5 days.
- h Record hospital and ICU discharge date on or before Day 29/Final Visit.
- i All laboratory tests and serum and plasma samples are required for all study subjects, regardless of treatment assignment. For subjects randomized to IVIG plus SMT all laboratory samples must be obtained prior to the Gammunex-C infusion on the designated day.
- j Cytokine panel includes IL-1 $\beta$ , IL-10, IL-6, IL-8 IL-2, interferon  $\gamma$ , and TNF- $\alpha$ . Note: serum samples must be stored at -70°C for later analysis at a reference laboratory.
- k During study infusions of Gammunex-C vital signs will be measured within 1 hour prior to the start of Gammunex-C infusion, 30 minutes after the start of infusion, and hourly through the end of Gammunex-C infusion.

